Randomization followed a participatory procedure successfully implemented in prior RCTs. At baseline, after completing questionnaires, one caregiver per family drew a piece of colored paper (yellow or green) from an opaque bag with equal distribution, ensuring balance across groups. One of the chiefs in each community then flipped a coin to determine which color corresponded to *BeThere* versus waitlist control. This process was repeated in each study community to maintain equal allocation across sites. The two-step method was designed to enhance transparency and community acceptance; previous studies using this approach showed no baseline imbalances and high follow-up rates in both arms.

Within families, a single index child aged 3–14 was randomly selected using a die-rolling procedure, proportionate to the number of eligible children. If the selected child was 7–14 years old, and both caregiver and child provided consent/assent, the child completed their own assessments at baseline, endline, and follow-up. Group assignments and index child selections were recorded in a master list maintained securely in War Child offices, with access restricted to the scientific and research coordinators.

11. Sample size

Sample size calculations were conducted using a joint significance estimator for indirect effects. Assuming a two-sided alpha of 0.05, an intervention–mediator error correlation of 0.2, mediator SD of 0.2, and error SD of 0.5, a sample of 425 caregivers per arm was sufficient to detect a mean difference of 0.4. Allowing for 10% attrition, the study aimed to enroll 960 caregivers (at least 480 families) and 400 index children across 40 intervention groups, providing adequate power to test multiple mediator models. In the end, we enrolled 956 caregivers and 328 index children.

12. Framework

The objective of the study has a superiority hypothesis testing framework. It aims to show the superiority of BeThere relative to the waitlist control condition on primary and secondary outcomes. In addition, through mediation analyses, this study aims to identify the mechanisms through which BeThere exerts an effect on child wellbeing.

13. Statistical interim analyses and stopping guidance

No interim analyses of study outcomes were planned or conducted. The Data Safety Management Committee reviewed adverse events throughout the study implementation and were responsible for determining whether any actions were required to reduce risk to study participants.

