21. Screening data

There were no diagnostic or clinical screening criteria for admission into the study.

22. Eligibility

The study aimed to enroll 960 caregivers and 400 children in Bor Country, South Sudan. Families were randomized to the BeThere intervention or waitlist control with 1:1 allocation and it is possible that more than one caregiver per family participated in the intervention. Randomization at the family-level ensured that caregivers from the same family were allocated to the same study arm. Individuals were eligible for the trial if they were:

- 1) Primary caregivers of children aged 3-14 years;
- 2) fluent in Dinka;
- 3) Living in Pariak, Ghoi, Taragok, Tibek, or Lenguet communities in Bor Country, Jonglei State, South Sudan; and 4) Willing to participate and commit to all nine sessions of BeThere.

For households with more than one caregiver, all caregivers must be willing to participate in order to be included. Individuals were excluded if they were less than 18 years of age, had participated in either a parenting or stress management intervention within the last six months, did not have a child aged 3-14 years, were unable to complete the assessment, were not fluent in Dinka, or were unwilling to give informed consent. One index child per household was randomly selected. If the selected index child was 7-14 years of age, they were also enrolled in the study and completed child-reported assessments at baseline, endline, and follow-up. If the index child was between 3-6 years of age, they did not complete an assessment. However, their caregivers were still enrolled and participated in study assessments. Not all households had more than one caregiver and/or an index child between the age of 7-14 years who agreed to participate.

[figure not shown]
23. Recruitment

Participants were recruited through community-based organizations, chiefs, and existing networks with whom War Child had established relationships. Recruitment methods included flyers, awareness sessions, door-to-door outreach, and word of mouth, and continued until the target of 192 participants per location was reached. Strategies used successfully in the pilot RCT were applied to engage male caregivers, such as scheduling around income-generating activities and tailoring messaging to their interests.

24. Withdrawal and loss to follow-up

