- **Parenting (caregiver-reported; primary outcome(s)):** Total score on a 24-item parenting scale developed to assess change in parenting. The total score combines subscales assessing parental warmth and sensitivity (17 items) and harsh parenting (six items). Parenting was assessed at baseline, endline, and follow up. Caregiver-reported parenting at endline will be considered the primary effectiveness outcome for the study.

Secondary outcomes

- **Parenting (child-reported; secondary outcome):** Total score on a 24-item parenting scale developed to assess change in parenting. The total score combines subscales assessing parental warmth and sensitivity (17 items) and harsh parenting (6 items). Child-reported parenting was assessed at baseline, endline, and follow up. The child does not report separately on multiple caregivers.
- **Caregiver psychological distress (secondary outcome):** Total score on the 10-item Kessler Psychological Distress scale. Caregiver psychological distress was assessed at baseline, midline, endline, and follow up.
- **Caregiver stress (secondary outcome):** Total score on the 18-item caregiver stress measure developed by War Child. Caregiver stress was assessed at baseline, midline, endline, and follow up.
- **Caregiver psychosocial wellbeing (secondary outcome):** Total score on the 14-item Warwick-Edinburgh Mental Wellbeing Scale. Caregiver psychosocial wellbeing was assessed at baseline, midline, endline, and follow up.
- **Child psychosocial wellbeing (caregiver-reported; secondary outcome):** Total score on the modified 25-item Kiddy-KINDL for Parents measure evaluating wellbeing specifically among the index child. A modified version of the KINDL for Parents was used that combines the Kiddy-KINDL (3-6 years) and Kid-KINDL (7-13 years) into a single measure. Child wellbeing was assessed at baseline, endline, and follow up.
- **Child psychosocial wellbeing (child-reported; secondary outcome):** Total score on the modified 25-item Kid-KINDL for Children. This measure is completed by index children ages 7-14 years only. Child psychosocial wellbeing was assessed at baseline, endline, and follow up.

Mediators

- **Group cohesion:** Total score on the 7-item Group Cohesiveness Scale. Group cohesion was assessed at midline, endline, and follow up.

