The analyses outlined in this strategy will be pragmatic, based on ITT and will utilize all available follow-up data from all randomised participants. The trial statistician will be blinded to treatment allocation. The main statistical analyses will establish the effectiveness of BeThere over waitlist control by comparing the mean difference of total parenting score at endline post randomization (see appendix).

Primary outcome

The primary outcome is the total score of the parenting scale at endline. We will compare randomized groups at endline and follow-up adjusted for baseline total score of parenting scale and account for hierarchical clustering of caregivers at the level of household. Specifically, we will fit a three-level random intercept linear regression model considering observations from endline and follow up at level 1, household at level 2 and community at level 3. The model will include the total score parenting scale at endline and follow up as the outcome variables with treatment group, baseline rate of parenting total score as explanatory variables. A time by treatment interaction will be included to allow the effect to differ at each time point (endline, follow up).

Secondary outcomes

Secondary outcomes as listed will be assessed with a similar methodology for the primary outcomes, using generalized linear mixed models with the appropriate link function/distribution. Normal outcomes will use an identity link function, binary variables would use a logit link function, and Poisson (count) variables would use a log link function. We will use all available time points in the model and extract differences at endline and follow up post-randomisation. All the questionnaires to be used have validated methods of scoring.

Method for handling non-compliance

In addition to the primary intention-to-treat analysis the effect of actually receiving treatment as defined in the protocol will also be estimated using a per-protocol analysis (PP). The PP analysis will remove data of those who:
attended fewer than seven sessions and any participant who did not complete all study assessments.

Planned sensitivity analysis

As a sensitivity analysis, we will replicate the effectiveness models excluding Community #1: Tibek due to implementation issues and delays. We will conduct subgroup analyses for the effectiveness models

stratified by gender of the caregiver, number of caregivers in the household (1 vs. 2), and child age (3-7 years vs. 8-14 years).

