Mediation Analyses

Estimate indirect effect of BeThere intervention on child wellbeing via caregiver wellbeing, caregiver distress, caregiver stress, and parenting.

Single mediator models. We will test for the effect of the BeThere intervention on each one of the multiple continuous mediators with the use of linear regression models. We chose a priori a p-value of lower than 0.15 to select the appropriate mediators to include in our final mediation analysis. We will test independence by examining partial correlations between our mediators after accounting for treatment allocation.

Full Structural Model. We will estimate a parametric structural equation model (sem package in Stata version 16.0 [StataCorp]) to estimate the total effect, the natural indirect effects (NIE), and natural direct effects (NDE) of Bethere on child wellbeing via caregiver wellbeing, caregiver distress, caregiver stress, and parenting. The NDE represented the effect of BeThere on Child Psychosocial Wellbeing (caregiver report) that was independent of caregiver wellbeing, caregiver distress, caregiver stress, and parenting. The NIE represents the proportion of BeThere intervention that could be explained by its effect on changes in caregiver wellbeing, caregiver distress, caregiver stress, and parenting. To quantify the magnitude of mediation, the study estimated the proportion of the effect mediated by caregiver wellbeing, caregiver distress, caregiver stress, and parenting ($NIE/[NDE + NIE]$). All analyses will be estimated using bootstrapping (500 replications) to recover the correct SEs for direct and indirect effects. Results are presented as coefficients and 95% confidence intervals (see appendix).

[figure not shown]
[figure not shown]

Figure 6 Primary mediation pathways

To assess the effect of group cohesion among beneficiaries in the BeThere intervention group on caregiver wellbeing and distress

First, we will examine the correlations among midline and endline group cohesion values with endline and follow-up caregiver wellbeing, stress, and distress.

We will use a structural equation model (SEM) to estimate the indirect effect of the BeThere intervention on caregiver outcomes through group cohesion. The model will specify caregiver wellbeing, caregiver stress, and caregiver distress at endline and follow-up as the outcomes using a similar method to that described above.

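### The mediation regressions, SEM and bootstrap specify no household clustering, so as written they do not deliver correct SEs for arm effects

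*SAP*

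**What the plan says.** Section 22 of the SAP describes the allocation: "Randomization at the family-level ensured that caregivers from the same family were allocated to the same study arm". It adds that "One index child per household was randomly selected". Section 26 defines the caregiver-reported KINDL as a "measure evaluating wellbeing specifically among the index child", and section 27a makes this caregiver report the outcome of the mediation model. A two-caregiver household can therefore supply two ratings of one child under one allocation.

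Section 27a treats this dependence differently in two places:

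- **Effectiveness models.** The primary model has a household level, and the secondary outcomes follow a similar method.
- **Mediation analyses.** Each mediator is tested by linear regression, with p below 0.15 as the rule for entering the final model. The structural model is a parametric SEM fitted with Stata's sem. On standard errors the text says: "All analyses will be estimated using bootstrapping (500 replications) to recover the correct SEs for direct and indirect effects". The group-cohesion SEM is to use a similar method.

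The mediation text mentions no household level, clustered variance or resampling unit, and does not restrict the analysis to one caregiver per household.

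**The concern.** A bootstrap reproduces the sampling variability of whatever unit it draws. If single caregiver records are drawn, as happens when no cluster is declared, the two members of a couple are drawn separately and the SE is the one that would hold if caregivers were independent. They are unlikely to be: they share an arm and a home, and for the outcome they describe the same child.

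Estimating the indirect effect on child wellbeing is primary objective 3 and the subject of one of the two planned manuscripts. Total, direct and arm-to-mediator effects would be reported with intervals that are too narrow, and the p<0.15 screen would admit more mediators that BeThere does not affect than its threshold suggests.

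**Working it through.** **The plan's own figure.** Section 11 gives 425 caregivers per arm and 10% attrition: 2 × 425 / 0.90 = 944.4, so 945. The stated target is 960, or 192 in each of five communities (5 × 192 = 960), which is 1.6% higher. The 425 itself cannot be confirmed because no power is stated. No ICC or design effect is given, so the SAP has no clustering figure to check against.

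**Inputs**

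- Caregivers per household: one or two (SAP subgroup definition and appendix variable list).
- Target: "the study aimed to enroll 960 caregivers (at least 480 families) and 400 index children across 40 intervention groups". Result: "In the end, we enrolled 956 caregivers and 328 index children". The number of enrolled households is not given.
- s, the share of caregivers in two-caregiver households: not given. I use s = 1 as the upper bound and s = 0.5 for comparison.
- ICC within household: not given. I assume 0.1, 0.3 and 0.5.

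**Arm effects.** With arm assigned by household and at most two caregivers in each, the variance of an arm contrast is multiplied by DE = 1 + s × ICC. The correct SE is √DE times the record-level SE. A nominal 5% two-sided test has actual error 2 × [1 − Φ(1.96/√DE)].

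| ICC | √DE, s = 1 | Error, s = 1 | √DE, s = 0.5 | Error, s = 0.5 |
|---|---|---|---|---|
| 0.1 | 1.05 | 6.2% | 1.02 | 5.6% |
| 0.3 | 1.14 | 8.6% | 1.07 | 6.8% |
| 0.5 | 1.22 | 11.0% | 1.12 | 8.0% |

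For example, at ICC 0.5 and s = 1, DE = 1.5, √1.5 = 1.225, 1.96/1.225 = 1.60, and the two-sided error is 11.0%. The 425 per arm then carry the information of 425/1.5 = 283 independent caregivers. Since DE cannot exceed 2, the SE ratio cannot exceed √2 = 1.41.

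**The mediator screen.** For p<0.15 the critical value is 1.44. At mediator ICC 0.3, 1.44/√1.30 = 1.26 gives 21% (s = 1), and 1.44/√1.15 = 1.34 gives 18% (s = 0.5).

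**Direct and indirect effects.** These were simulated in a one-mediator model with both paths set to 0.3, mediator ICC 0 to 0.3 and outcome ICC 0.1 to 0.7. Each entry is the true sampling SD divided by the caregiver-level bootstrap SE, with Monte Carlo noise of about 5%.

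| Effect | 480 households, all with two caregivers | 640 households, half with two caregivers |
|---|---|---|
| Direct and total | 1.05 to 1.28 | 1.03 to 1.19 |
| Indirect, mediator ICC 0.2 to 0.3 | 1.06 to 1.11 | 1.07 to 1.09 |
| Indirect, mediator ICC 0 to 0.1 | 0.95 to 0.97 | 0.95 to 1.04 |

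In the second setting half of the households are pairs, which puts two thirds of caregivers in pairs (640 of 960). Resampling households instead brought all ratios back to about 1 (0.93 to 1.07).

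**The case against.** The strongest reply is that this is an omission. A reader might infer that the plan assumes independent caregivers, but it nowhere says so; it leaves the resampling unit open, and an analyst could cluster by household without departing from the text. That is fair as to wording. It does not settle the matter, because the named method with default settings draws single records, and the text asserts that this yields correct SEs.

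Four stronger readings are tempting and are not supported:

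- **Most households have two caregivers.** The figure of 480 families is a floor, reached only if every household has two. Section 22 says that not all households had more than one caregiver. The s = 1 column is therefore an upper bound.
- **Mediation will be falsely claimed on a large scale.** The largest ratios concern the total and direct effects, and a falsely significant direct effect is not a claim of mediation. Simulating a joint-significance test of the indirect effect with unclustered SEs (860 caregivers, all in pairs, mediator ICC 0.3, outcome ICC 0.5) gave an error of about 0.5% when both paths are null. It gave about 8% to 9% when only the arm-to-mediator path is null, and 6.5% to 7% when only the mediator-to-outcome path is null. Inflation exists but is modest.
- **500 replications is an error.** The SAP uses the bootstrap for SEs and never specifies percentile limits. The Monte Carlo error of a bootstrap SE at 500 replications is about 1/√(2 × 500) = 3%.
- **The two papers will show conflicting SEs because of this gap.** One uses a baseline-adjusted mixed model over two time points and the other an SEM. Their SEs would differ even with household clustering in both.

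**Conclusion.** The point holds and should be fixed. As written, the mediation analyses lack the household structure that the same section applies to the effectiveness models, and the claim about SEs is not supported. With positive within-household correlation, SEs for the total and arm-to-mediator effects are too small by √(1 + s × ICC), and the direct effect is affected similarly. The indirect effect is affected less, and hardly at all if mediators are nearly uncorrelated within households.

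The direction rests only on that positive correlation, which two ratings of one child make likely for the outcome. The size is uncertain, because neither s nor the ICC is in the SAP. The primary outcome analysis is untouched.

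**What to change.** In section 27a, state that:

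1. bootstrap SEs and confidence intervals for the mediation SEM come from resampling households, stratified by community and arm;
2. the single-mediator regressions, including the p<0.15 screen, use household-clustered variance;
3. the group-cohesion SEM is handled in the same way.

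More replications are optional. The household identifier is already in the planned dataset, so the cost is a sentence or two in the SAP and slightly wider intervals. Reporting the number of one- and two-caregiver households would let readers judge how much the clustering matters.

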Parenting interventions in conflict-affected settings have often assumed that poor parenting stems mainly from a lack of knowledge or skills. However, research shows that caregiver stress and mental health challenges—driven by war exposure and daily stressors—play a central role in sub-optimal parenting. The family stress model highlights how caregiver wellbeing mediates the impact of conflict on parenting, with negative consequences for children’s psychosocial health. Studies further show that caregivers themselves are frequently perpetrators of abuse in emergencies, and that caregiver mental health is directly linked to child mental health outcomes among conflict-affected and displaced populations.

To address these interconnected factors, War Child developed *BeThere*, a nine-session preventive group intervention for caregivers of children aged 3–14 affected by armed conflict and forced migration. Grounded in the family stress model, the program combines parenting support with a strong focus on caregiver mental health. The first four sessions emphasize caregiver mental health and stress management, followed by sessions on positive parenting in adversity, with a final review session. Through this dual focus—building evidence-based parenting skills and strengthening caregiver mental health—*BeThere* seeks to improve both parenting practices and child wellbeing.

8. Objectives

The overall objective of this study is to evaluate the effectiveness of BeThere for improving parenting behaviors and child wellbeing in Bor County, South Sudan. The research objectives are as follows:

Primary Objectives

1. To evaluate the effectiveness of the BeThere intervention in improving parenting among participating caregivers in a fully-powered trial in South Sudan
2. To evaluate the effects of the BeThere intervention on participating caregivers’ children using child-reported outcomes among a subsample of children aged 7-14.
3. To estimate the indirect effect of the BeThere intervention via caregiver wellbeing, caregiver distress, caregiver stress, and parenting on child wellbeing.

Secondary Objective

4. To assess the effect of group cohesion among beneficiaries in the BeThere intervention group on caregiver wellbeing and distress

SECTION 3: STUDY METHODS

9. Trial design

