14. Timing of final analysis

All analyses will be conducted after completion of data collection for the trial. The statistician and PI will be masked to study condition during data collection, cleaning, and the primary effectiveness analyses. Secondary analyses examining mediators that relate to intervention group characteristics (e.g., BeThere Mechanism of Action, Group Cohesion) or require analysis of intervention midline assessment data will be conducted after effectiveness analyses are finalized to preserve masking.

15. Timing of outcome assessments

Data used for this study will be collected by research assistants at baseline, midline (BeThere session 5), endline (within 2-3 weeks following session 9 or approximately 10-12 weeks post-enrollment), and follow-up (12 weeks after completion of the final session or approximately 22 weeks post-enrollment). The midline assessment was only administered to the experimental (i.e., BeThere) group and not to the waitlist control group.

SECTION 4: STATISTICAL PRINCIPLES

16. Level of statistical significance

A significance level of $\alpha=0.05$ will be applied.

17. Adjustments for multiplicity

We do not plan to adjust for multiple testing.

18. Confidence intervals

Results will be presented as coefficients and 95% CIs.

19. Adherence and protocol deviations

Participant adherence to the intervention will be measured using intervention session attendance records. Completion of the intervention will be defined as having attended seven or more sessions. We will report the mean (SD) and median (IQR) number of sessions attended in the BeThere group.

Facilitator fidelity to the intervention will be measured using a fidelity checklist. We will report the mean (SD) and median (IQR) scores on the fidelity checklist as an indicator of trial implementation quality.

Any major deviations from the protocol will be reported in the main outcomes paper.

20. Analysis populations

The primary analysis will be conducted on the intent-to-treat sample, meaning that all participants will be included and analyzed as randomized. No enrolled participants were excluded from the main analytic sample. We will also conduct a per protocol analysis including waitlist control participants who completed all assessments and did not participate in any BeThere intervention components and only BeThere intervention participants who completed seven or more intervention sessions and did not drop out of the study.

SECTION 5: TRIAL POPULATION

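### 500 bootstrap replications leave the 5% verdict on borderline mediation effects open to the random seed; at least 5,000 with a stated seed would remove most of this at almost no cost (minor)

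*SAP*

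**What the plan says.** Section 8 of the SAP makes mediation a primary objective: "To estimate the indirect effect of the BeThere intervention via caregiver wellbeing, caregiver distress, caregiver stress, and parenting on child wellbeing". Section 27a (Mediation Analyses, Full Structural Model) sets the source of uncertainty for that analysis: "All analyses will be estimated using bootstrapping (500 replications) to recover the correct SEs for direct and indirect effects". The models for group cohesion later in section 27a follow the same approach.

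Section 16 says "A significance level of $\alpha=0.05$ will be applied", section 17 says "We do not plan to adjust for multiple testing", and section 18 says "Results will be presented as coefficients and 95% CIs". The SAP states no seed, does not say whether intervals are normal-based, percentile or bias-corrected, and sets no target for Monte Carlo error. The wording assigns the bootstrap the task of supplying SEs. Percentile limits are not mentioned.

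Mediators enter the final model by a separate rule: "We chose a priori a p-value of lower than 0.15 to select the appropriate mediators to include in our final mediation analysis". That rule uses linear regression and, as written, not the bootstrap.

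**The concern.** A bootstrap SE or interval has two kinds of error: sampling error, which the trial cannot avoid, and Monte Carlo error, which depends only on the number of replications and the seed. At 500 replications the second kind is small but not negligible for a result close to the 5% boundary. Two analysts with the same data and model could then report different verdicts on the same indirect effect.

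The mediation results are the subject of the second planned manuscript, and several are reported: four mediators in the table shell (Appendix 1, item 4), the direct and total effects, a serial model, and the cohesion models. The more estimates there are, the greater the chance that at least one is borderline. Without a stated seed, the choice between runs that differ also stays open.

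**Working it through.** **Inputs.** From the SAP: B = 500 replications, 95% CIs, alpha 0.05 (two-sided in section 11), four candidate mediators. Assumed: an approximately normal bootstrap distribution, and B = 5,000 as the comparison. The figure of 500 is a chosen setting with no derivation, so there is nothing to reproduce.

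**1. Monte Carlo error of a bootstrap SE.** Coefficient of variation = 1/√(2(B−1)).
- B = 500: 1/√998 = 0.0317, or 3.2%. A 95% range is about ±1.96 × 3.2% = ±6.2%.
- B = 5,000: 1/√9,998 = 0.0100, or 1.0%.

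**2. Monte Carlo error of a percentile limit, if that interval is used.** SD of the tail area = √(0.025 × 0.975/B). Dividing by the normal density at 1.96 (0.0584) gives the error in units of the effect's SE.
- B = 500: 0.0070/0.0584 = 0.12 SE.
- B = 5,000: 0.0022/0.0584 = 0.038 SE.

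**3. Band of p-values in which the verdict can change with the seed.** For SE-based intervals the band is z = 1.96 × (1 ± 1.96 × CV). For percentile intervals it is z = 1.96 ± 1.96 × (limit error).

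| B | SE-based: z | SE-based: p | Percentile: z | Percentile: p |
|---|---|---|---|---|
| 500 | 1.84 to 2.08 | 0.066 to 0.037 | 1.73 to 2.19 | 0.084 to 0.028 |
| 5,000 | 1.92 to 2.00 | 0.055 to 0.046 | 1.89 to 2.03 | 0.059 to 0.042 |

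**4. Probability that one run falls on the wrong side of 5%, judged against unlimited replications.**
- SE-based, p = 0.04 (z = 2.054): the verdict is lost if the bootstrap SE is too large by a factor above 2.054/1.96 = 1.048. From the chi-square distribution of the variance with 499 degrees of freedom, the probability is 6.4%.
- SE-based, p = 0.06 (z = 1.881): the verdict is wrongly gained if the factor is below 1.881/1.96 = 0.960. The probability is 10.3%.
- SE-based, p = 0.03 and p = 0.07: 0.0% and 0.8%.
- Percentile, p = 0.04: the number of draws beyond zero is Binomial(500, 0.02). The probability that it exceeds 0.025 × 500 = 12.5 is 21%.
- Percentile, p = 0.06: Binomial(500, 0.03) falls at 12 or below with probability 26%.
- With 5,000 replications the SE-based figures are about 0%. The percentile figures are below 1% and 1.9%.

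The percentile figures shift somewhat with the quantile convention. Simulation with interpolated quantiles gave about 16% at p = 0.04 and 30% at p = 0.06 for B = 500.

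**5. Several mediators together.** The SAP gives no effect sizes for individual paths, so any rate rests on assumptions. The simulations took n = 860, four mediators correlated 0.5, no clustering, and two independent runs per simulated trial. The outcome was disagreement on at least one of five indirect effects (four plus their total). Here a is the effect of BeThere on each mediator and b the effect of each mediator on child wellbeing.

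| Assumed a, b | SE-based, B = 500 | Percentile, B = 500 |
|---|---|---|
| 0.40, 0.25 | 0% | 0% |
| 0.40, 0.20 | 0.7% | 0% |
| 0.10, 0.05 | 4% | 11% |
| 0.25, 0.08 | 12% | 12% |
| 0.20, 0.10 | 13% | 18% |
| 0.20, 0.12 | 27% | 22% |

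At a = 0.20, b = 0.12 the approximate z of each indirect effect is 2.02, almost on the threshold, and disagreement per effect was only 5 to 6%. The settings used 60 to 150 trials each, so single rates are uncertain by a few percentage points. With 5,000 replications, the near-threshold settings (a = 0.15 to 0.25, b = 0.08 to 0.15) gave roughly 3 to 9%.

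**The case against.** The best defence is that the SAP uses the bootstrap to obtain SEs, and an SE known to about 3% is good enough for that. This stands. On that reading the larger percentile figures (21% and 26%) do not apply, and 6% and 10% are the relevant ones. They are shown side by side only because the SAP does not name the interval type.

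The defence can add that results are to be read as coefficients with CIs, that no rule in the SAP adds or drops a mechanism by bootstrap significance, and that a seed is normally fixed in the analysis code. The first two are fair and limit the harm, although section 16 does apply a 5% level. The third is common practice, but a seed fixed in advance leaves no choice between runs. Some seed-sensitive band remains at any finite number of replications: an effect at exactly p = 0.05 stays a coin toss.

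A reader might infer that the set of mediators entering the model depends on the seed. The SAP does not support that, because the p<0.15 screen is a linear regression. A reader might also take a disagreement rate of up to 27% as the expected behaviour of the plan. It describes only the case where all four mediators sit near the threshold, and nothing in the SAP says they will.

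**Conclusion.** The point holds as a minor one. Five hundred replications give a 3.2% Monte Carlo error in each SE, and the 5% verdict can depend on the seed only for p of about 0.037 to 0.066 (SE-based) or 0.028 to 0.084 (percentile). These bands assume an approximately normal bootstrap distribution. For several mediators jointly, the rate at which two runs disagree ranges from about 0% with strong effects to roughly 10 to 27% when all lie near the threshold; that range rests on assumed effect sizes.

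It would be going too far to conclude that the mediation analysis is unreliable or that Objective 3 is compromised. Effects clearly away from 5% are unaffected, and so is the primary effectiveness analysis, for which the SAP specifies a mixed model without a bootstrap.

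**What to change.** In section 27a (Full Structural Model), replace 500 with at least 5,000 replications and state a fixed seed. Apply both to the child-wellbeing mediation models and to the cohesion models that follow the same approach. Naming the interval type in the same sentence would settle which band applies. Both changes are needed: a seed alone makes one noisy run reproducible, and more replications alone leave the choice of run open.

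The cost is one number and a seed in the text, plus computing time for linear models on about 950 caregivers (956 enrolled). No new data are needed, and there is no statistical drawback.
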